8.3. Final Analysis of Efficacy Outcomes

Interim efficacy analyses will not be repeated but will be included in the final report. Any changes to the data that was sequestered and analyzed for interim will be summarized and explained. In addition, the following objectives will be explored:

- Evaluate change from baseline in WOMAC total score for the target knee at Weeks 39 and 52
- Evaluate change from baseline OA function in the target knee as assessed by the WOMAC function subscore at Weeks 39 and 52
- Evaluate change from baseline OA in the target knee as assessed by the WOMAC Total at Weeks at Weeks 39 and 52
- Evaluate change from baseline OA disease activity as assessed by the Patient Global Assessment at Weeks 39 and 52
- Evaluate change from baseline in medial and lateral JSW as documented by X-ray of the target knee at Week 52
- Determine the percentage of Outcome Measures in Rheumatology Clinical Trials (OMERACT)-Osteoarthritis Research Society International (OARSI) responders and “strict” responders at Weeks 39 and 52
- Evaluate change from baseline OA disease activity as assessed by the Physician Global Assessment at Weeks 39 and 52
- Evaluate change from baseline health-related quality of life (HRQOL) as assessed by the 36-Item Short Form Health Survey (SF-36) at Weeks 4, 13, 26, 39 and 52

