3.1.3. Exploratory Endpoints

Exploratory efficacy will be assessed by evaluating changes from baseline WOMAC total score, HRQOL as assessed by SF-36, and Physician Global Assessment at all timepoints, as well as by

evaluating the percentage of OMERACT-OARSI responders and “strict” responders at Weeks 13, 26, and 52 (Pham et al. 2003) and change in lateral JSW as evaluated by X-ray at Week 26 and 52 and medial JSW at Week 52. Additionally, efficacy will be assessed by evaluating changes from baseline WOMAC pain and function subscores and Patient Global Assessment at Weeks 4, 39, and 52.

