1.3. Exploratory Objectives

Additional exploratory objectives of this study include:

- Evaluate change from baseline in WOMAC total score for the target knee at Weeks 4, 13, 26, 39 and 52
- Evaluate change from baseline OA pain in the target knee as assessed by the WOMAC pain subscore at Weeks 4, 39 and 52
- Evaluate change from baseline OA function in the target knee as assessed by the WOMAC function subscore at Weeks 4, 39 and 52
- Evaluate change from baseline OA disease activity as assessed by the Patient Global Assessment at Weeks 4, 39 and 52
- Evaluate change from baseline in medial JSW as documented by X-ray of the target knee at Week 52
- Evaluate change from baseline in lateral JSW as documented by X-ray of the target knee at Weeks 26 and 52

- Determine the percentage of Outcome Measures in Rheumatology Clinical Trials (OMERACT)-Osteoarthritis Research Society International (OARSI) responders and “strict” responders at Weeks 4, 13, 26, 39 and 52
- Evaluate change from baseline health-related quality of life (HRQOL) as assessed by the 36-Item Short Form Health Survey (SF-36) at Weeks 4, 13, 26, 39 and 52
- Evaluate change from baseline OA disease activity as assessed by the Physician Global Assessment at Weeks 4, 13, 26, 39 and 52

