8.1.1. ANCOVA Model for Continuous Efficacy Outcomes

ANCOVA models will be used for all continuous efficacy outcome measures summarized by change from baseline in order to test the following three hypotheses:

$$H_0: (\beta_i - \beta_0) = 0$$

$$H_A: (\beta_i - \beta_0) \neq 0, \text{ where } i = 1,2,3$$

In the statement above, β is the least squares estimate in the change in the continuous efficacy outcome from baseline at each timepoint (where β_0 is the estimate for placebo), and i represents each of the three SM04690 treatment groups.

Least squares estimate of difference between each treatment group and placebo in the change in the continuous efficacy outcome from baseline at each timepoint, adjusted for baseline value, will be reported along with unadjusted 95% confidence intervals and P values.

Continuous efficacy measures to be analyzed by the ANCOVA model include:

- WOMAC Pain
- WOMAC Function
- WOMAC Total
- Patient Global Assessment
- Physician Global Assessment
- Medial and Lateral Joint Space Width
- SF-36

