8.2. Interim Analysis of Efficacy Outcomes

Analysis of all endpoints in support of the primary and secondary objectives will be conducted after all subjects complete the Week 26 visit but prior to the formal completion of the trial at 52 weeks.

This will include:

- Evaluate change from baseline OA pain in the target knee as assessed by the WOMAC pain subscore at Weeks 13 and 26
- Evaluate change from baseline OA function in the target knee as assessed by the WOMAC function subscore at Weeks 13 and 26
- Evaluate change from baseline OA disease activity as assessed by the Patient Global Assessment at Weeks 13 and 26
- Evaluate change from baseline in medial joint space width (JSW) as documented by X-ray of the target knee at Week 26

Additionally, endpoints in support of exploratory objectives will also be analyzed, including:

- Evaluate change from baseline OA pain in the target knee as assessed by the WOMAC pain subscore at Week 4
- Evaluate change from baseline OA function in the target knee as assessed by the WOMAC function subscore at Week 4
- Evaluate change from baseline in WOMAC total score for the target knee at Weeks 4, 13 and 26
- Evaluate change from baseline OA disease activity as assessed by the Patient Global Assessment at Week 4
- Evaluate change from baseline in lateral JSW as documented by X-ray of the target knee at Week 26
- Determine the percentage of Outcome Measures in Rheumatology Clinical Trials (OMERACT)-Osteoarthritis Research Society International (OARSI) responders and “strict” responders at Weeks 4, 13 and 26
- Evaluate change from baseline OA disease activity as assessed by the Physician Global Assessment at Weeks 4, 13 and 26

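### Does the final-analysis list in SAP 8.3, which repeats WOMAC Total and omits WOMAC Pain, drop pain at Weeks 39 and 52?

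*SAP*

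**What the plan says.** SAP 8.3 carries the interim results into the final report unrepeated and then adds a list, introduced by "In addition, the following objectives will be explored". The first bullet of that list is "Evaluate change from baseline in WOMAC total score for the target knee at Weeks 39 and 52". The third is "Evaluate change from baseline OA in the target knee as assessed by the WOMAC Total at Weeks at Weeks 39 and 52". The other bullets cover WOMAC Function, Patient Global, medial and lateral JSW, the two OMERACT-OARSI responder measures, Physician Global and SF-36. WOMAC Pain does not appear.

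SAP 8.2, the other list with named weeks, covers pain in two bullets: "Evaluate change from baseline OA pain in the target knee as assessed by the WOMAC pain subscore at Weeks 13 and 26" and, among the exploratory items, "Evaluate change from baseline OA pain in the target knee as assessed by the WOMAC pain subscore at Week 4".

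The objectives go further. SAP 1.3 has "Evaluate change from baseline OA pain in the target knee as assessed by the WOMAC pain subscore at Weeks 4, 39 and 52", and Protocol 2.2 has the same objective. Protocol 3.1.3 makes it an endpoint: "evaluating changes from baseline WOMAC pain and function subscores and Patient Global Assessment at Weeks 4, 39, and 52".

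The model is set in SAP 8.1.1. It applies ANCOVA to all continuous efficacy outcomes and puts WOMAC Pain first among them. It says the least squares difference between each dose and placebo "in the change in the continuous efficacy outcome from baseline at each timepoint, adjusted for baseline value, will be reported", together with unadjusted 95% confidence intervals and P values.

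**The concern.** WOMAC Pain at Week 13 is the primary endpoint, so whether any pain effect lasts to one year is an obvious question for the final report. The two SAP sections that assign analyses to a reporting stage by week leave that outcome out at the two late visits, while one of them lists WOMAC Total at those visits twice. A programmer working only from 8.2 and 8.3 would produce no late pain comparison.

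Timing adds to the worry. Protocol 3.2.4 unblinds the sponsor once all subjects have completed Week 26, so a gap over the later visits could leave room to decide on late pain with the earlier results known. At stake would be six exploratory comparisons in each analysis set.

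**Working it through.** There is no figure in the plan to reproduce. The check matches the outcome-by-visit pairs set as objectives (SAP 1.1 to 1.3) against those listed for analysis (SAP 8.2 and 8.3). The two responder definitions are counted as one outcome and SF-36 as one.

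| Outcome | Set in SAP 1.1–1.3 | Listed in 8.2 | Distinct in 8.3 | Not listed |
|---|---|---|---|---|
| WOMAC Pain | 5 | 3 | 0 | 2 (Weeks 39, 52) |
| WOMAC Function | 5 | 3 | 2 | 0 |
| WOMAC Total | 5 | 3 | 2 (each stated twice) | 0 |
| Patient Global | 5 | 3 | 2 | 0 |
| Physician Global | 5 | 3 | 2 | 0 |
| OMERACT-OARSI | 5 | 3 | 2 | 0 |
| SF-36 | 5 | 0 | 5 | 0 |
| Medial JSW | 2 | 1 | 1 | 0 |
| Lateral JSW | 2 | 1 | 1 | 0 |
| Sum | 39 | 20 | 17 | 2 |

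The two lists do not overlap, so 20 + 17 = 37 pairs are listed and 39 − 37 = 2 are missing. Counting the two responder definitions separately adds five pairs to both sides: 44 set, 42 listed, still 2 missing. The gap is therefore exactly pain at Weeks 39 and 52, and WOMAC Total at the same weeks is the only duplicate.

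Comparisons behind the gap: 3 doses × 2 visits = 6 per analysis set. SAP section 8 runs efficacy on ITT, mITT and PP, so 6 × 3 = 18 in all. None is in H1 to H21, because that sequence in SAP 8.2.1 ends with Week 26 endpoints.

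Next, whether the analysis is specified without 8.3:

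1. *Outcome and model.* SAP 8.1.1 names WOMAC Pain and fixes the model: ANCOVA on change, adjusted for the baseline value, each dose against placebo. The wording is mandatory.
2. *Weeks.* 8.1.1 says only that the result is given for each timepoint. The timepoints follow from SAP 1.3, which names Weeks 39 and 52 for pain, and from Protocol Appendix 1, which marks WOMAC at both visits.
3. *Descriptive results.* SAP 8.1 calls for summaries of continuous outcomes, and of their change, at every visit, and for subject-level listings of every outcome in the final report.
4. *Data.* Protocol 5.8 collects WOMAC at all visits. The responder analysis that 8.3 does list at Weeks 39 and 52 needs the pain subscore (SAP 3.2.2), so it must be derived at those visits anyway.
5. *Exclusion.* Nothing in 8.3 limits the final analysis to its list.

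Finally, the form of the duplicate bullet. "Evaluate change from baseline OA in the target knee as assessed by the WOMAC Total at Weeks at Weeks 39 and 52" follows the sentence pattern used for the pain and function objectives, but the word naming the domain is missing and two words are doubled. The WOMAC Total objective is phrased differently, as "Evaluate change from baseline in WOMAC total score for the target knee at Weeks 39 and 52" shows. That points to a pain bullet in which the wrong score was typed. This is an inference, and the conclusion does not need it.

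**The case for a change.** The best case for a change is that general text does not make a faulty list right. Sections 8.1, 8.1.1 and Protocol 10.5.5 name no weeks, and the two sections that schedule analyses by week leave these two out. Because the interim analyses are not repeated, Weeks 39 and 52 are the only new pain comparisons the final report can offer. With the sponsor unblinded by then, a plan that could be cited either way gives discretion, and one replaced line would remove it at almost no cost.

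The factual part stands: the list has one duplicate and one omission, and correcting it would be good housekeeping. The part about discretion is weak. Leaving late pain out could not be defended from the SAP as a whole, because it would go against the reporting requirement in 8.1.1 and leave a stated objective (SAP 1.3) and a protocol endpoint (3.1.3) unreported. Reporting it needs no choice of outcome, model or visit, since all three are already fixed. The absence of week numbers in 8.1.1 matters little when the same SAP gives them for pain in 1.3.

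**Conclusion.** No change to the plan is needed. SAP 8.3 contains a clerical slip, which touches two outcome-by-visit pairs: six exploratory comparisons per analysis set, 18 across the three sets. The rest of the SAP already requires those comparisons, so correcting the bullet would change no result, conclusion, confirmatory test, power figure or data collection.

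This rests on two readings. First, each timepoint in 8.1.1 covers every visit at which WOMAC is scheduled and set as an objective. Second, the list in 8.3 adds to the general analysis rules and does not replace them, as "In addition, the following objectives will be explored" suggests. If 8.3 were instead taken as a complete and closed list, the late pain comparisons would be missing from the final report, but even then only exploratory results would be affected.

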9. ANALYSIS SOFTWARE

All data processing, summarization and analyses will utilize SAS® Version 9.4. QualityMetric Health Outcomes Scoring Software 4.5 will be used to score SF-36 questionnaires.

